## 10.0 Effectiveness Analysis

### 10.1 General Considerations

#### Analysis Set Used for Effectiveness Analyses

The ITT set will be used for the effectiveness analysis.

#### Descriptive Analyses

The primary and all secondary effectiveness variables will be described by statistical characteristics. Categorical data will be described by frequency and percentage, quantitative data by mean, standard deviation, minimum, first quartile, median, third quartile and maximum. Also the number of non-missing values will be given.

All analyses including the confidence intervals calculated will be of a descriptive sense.

No imputation of missing values will be done, data will be reported as observed.

### 10.2 Primary Effectiveness Analysis

RSV hospitalization is the primary effectiveness variable in this study. The following definitions will be applied:

### Respiratory and Cardiac Hospitalizations

A respiratory/cardiac hospitalization is defined as a hospital admission for the primary reason to evaluate or treat a respiratory/cardiac condition occurring after the first dose of palivizumab injection through 30 days after the last dose of palivizumab injection. New onset of respiratory/cardiac symptoms in an already hospitalized child, with an objective measure of worsening respiratory/cardiac status will also be considered as a cardiac/respiratory hospitalization.

### RSV Hospitalizations

An RSV hospitalization is defined as either 1) a respiratory/cardiac hospitalization with a positive RSV test, 2) new onset of respiratory/cardiac symptoms in an already hospitalized child, with an objective measure of worsening respiratory/cardiac status and a positive RSV test, or 3) death, which can be demonstrated as caused by RSV (by autopsy or clinical history and virologic evidence). To be considered a valid RSV test, the respiratory secretions for the RSV detection must have been collected within 2 days of admission or of worsening of respiratory/cardiac symptoms, respectively.

A hospital admission or a new onset of nosocomial respiratory/cardiac symptoms without an RSV test result will not be counted as RSV-hospitalization in the primary analysis.

Only RSV-associated hospital admissions, new onset of nosocomial respiratory/cardiac symptoms with a positive RSV test, and RSV-associated deaths occurring from the first dose of study drug injection to within 30 days of the last study drug dose will be included in the analyses for the primary endpoint.

The primary analysis will be the calculation of the number and proportion of subjects with RSV hospitalization along with the two-sided 95% exact confidence interval according to Clopper Pearson for the proportion.

In addition, a cross tabulation of reason for hospitalization or type of illness for already hospitalized subjects with new onsets of nosocomial respiratory/cardiac symptoms

[cardiac, respiratory, both] versus result of RSV text [positive, negative, not performed] will be done.

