5.0 Investigational Plan

5.1 Overall Study Design and Plan: Description

This is a Phase 3b, prospective, multicenter, open-label, non-controlled clinical study of immunoprophylaxis with Synagis[®] (Palivizumab) solution for injection for the prevention of severe lower respiratory tract RSV infection in infants at high-risk.

Approximately 50 subjects will be enrolled into the study in approximately 20 study sites in the Russian Federation and the Republic of Belarus. The target enrollment number for each of the subpopulations of CHD, BPD and pre-terms is a minimum of approximately 5 subjects.

Enrollment will start in November 2016 and will continue to no later than January 2017. All enrolled subjects will receive 15 mg/kg Synagis[®] (Palivizumab) solution by intramuscular (IM) injection every 30 days for a minimum of 3 and a maximum of 5 injections during the RSV season defined as November 2016 through March 2017. Children who undergo cardiac surgery with cardiopulmonary bypass through Study Day 150 should receive an additional replacement injection of study drug immediately following the surgery when determined by the physician to be medically stable for an intramuscular (IM) injection. Any subsequent doses of study drug will continue to be given according to the protocol-specified dosing schedule as described in Section 5.5. Each injection of palivizumab will occur at the study site and prior to each injection subjects will undergo safety assessments. Follow-up telephone calls with parent(s)/legal guardian(s) of all subjects that received at least one palivizumab injection will occur 30 and 100 days after their last injection of palivizumab.

All cardiac/respiratory hospitalizations or deterioration in the cardiac/respiratory status in a hospitalized infant will be evaluated by testing respiratory secretions using a validated real-time RT-PCR RSV diagnostic test to determine if RSV contributed to the hospitalization or deterioration.

The study was designed to enroll approximately 50 subjects to meet scientific and regulatory objectives without enrolling an undue number of subjects in alignment with ethical considerations. Therefore, if the target number of subjects has been enrolled, there is a possibility that additional subjects in screening will not be enrolled in the study.

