5.5.4 Selection and Timing of Dose for Each Subject

All subjects will receive palivizumab 15 mg/kg IM every 30 days. A ± 5 -day allowance window is permitted, except for the Visit 2 (Day 30), where only -5 -day window is allowed. Subjects will receive at least 3 and a maximum of 5 monthly injections of palivizumab during the 2016 – 2017 RSV season. Palivizumab may be administered at any time during the visit day. All study visit assessments must be performed prior to palivizumab IM injection. Vital signs will be measured before dosing and 30 min after study drug injection. The Investigator/designee will check for any AEs after study drug injection at the visit.

The number of individual doses is determined by the month of enrollment in [Table 1](#).

Table 1. Subject Dosing Timeline

November 2016	December 2016	January 2017	February 2017	March 2017	Total Doses ^a
Visit 1	Visit 2	Visit 3	Visit 4	Visit 5	5
	Visit 1	Visit 2	Visit 3	Visit 4	4
		Visit 1	Visit 2	Visit 3	3

a. An extra dose of palivizumab will be administered in the event of a cardiac surgery with cardiopulmonary bypass surgery.

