### **4.3 Sample Size**

No formal sample size calculation was performed for this descriptive study and the sample size is based primarily on practical considerations. It is anticipated that approximately 50 subjects will be enrolled. With a sample size of 50 subjects, the width of the 95% exact confidence interval in case of 0, 1, 2, 3 RSV hospitalizations (i.e., event rates of 0%, 2%, 4%, 6%) would be 7.1% (lower bound 0%; upper bound 7.1%), 10.6% (0.1%; 10.6%), 13.2% (0.5%; 13.7%), 15.3% (1.2%; 16.5%), respectively.

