## **5.0 Analysis Populations**

### **5.1 Definition of Analysis Populations**

All analyses will be performed on the intent-to-treat (ITT) set, defined as all enrolled subjects who received at least one dose of study drug, unless otherwise indicated.

The safety analyses will be performed on the safety set which is identical to the ITT set.

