## **8.0 Patient Disposition**

The number of subjects for each of the following categories will be summarized overall and by country and site:

- Subjects enrolled
- Subjects received at least one dose of study drug
- Subjects who prematurely discontinued study drug
- Subjects who completed study drug
- Subjects who prematurely discontinued the study
- Subjects who completed the study
- Subjects enrolled in first month of RSV season (November)
- Subjects enrolled in second month of RSV season (December)
- Subjects enrolled in third month of RSV season (January)

For the ITT set, the number and percentage of subjects who discontinued study drug or who discontinued from the study, respectively, will be summarized by reason (primary or secondary) and by primary reason.

Furthermore, the following information will be summarized for the ITT set:

- Number of patients observed per visit (*also broken down by enrollment month*)
- Protocol deviations (four major ICH deviations)

- Inclusion/exclusion criteria met [yes, no] based on the inclusion/exclusion module of the CRF
- Specification of violated inclusion/exclusion criteria based on the inclusion/exclusion module of the CRF
- Subject developed withdrawal criteria but was not withdrawn [yes, no]
- Subject received wrong treatment or incorrect dose [yes, no]
- Subject received excluded concomitant treatment during the treatment with palivizumab [yes, no]

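### Does the primary RSV-hospitalization proportion need a time-at-risk rate beside it, since it pools nominal windows of 150, 120 and 90 days?

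*SAP*

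**What the plan says.** SAP 10.2 takes as its primary result the number and proportion of children with an RSV hospitalization, with a two-sided 95% Clopper-Pearson interval. One sentence sets the time limit for admissions, in-hospital onsets and deaths alike; it ends "deaths occurring from the first dose of study drug injection to within 30 days of the last study drug dose will be included". The denominator is the ITT set of SAP 5.1, "defined as all enrolled subjects who received at least one dose of study drug".

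The length of that window depends on when a child enters. Protocol 5.1 says "Enrollment will start in November 2016 and will continue to no later than January 2017". Protocol 5.5.4 says "The number of individual doses is determined by the month of enrollment in" its Table 1, which gives five doses for November entry, four for December and three for January. Protocol 5.1 can lengthen the window further: "Children who undergo cardiac surgery with cardiopulmonary bypass through Study Day 150 should receive an additional replacement injection of study drug".

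SAP 4.3 states precision by event count alone, as "the width of the 95% exact confidence interval in case of 0, 1, 2, 3 RSV hospitalizations". SAP 10.4 (other effectiveness analyses) and SAP 10.6 (effectiveness subgroups) are marked not applicable, so neither a rate nor a split of the endpoint by entry month is planned. SAP 8.0 does report enrollment by month and discontinuations by reason. SAP 9.0 reports doses and duration of exposure by enrollment month, with duration running to 100 days after the last injection. SAP 10.1 adds: "All analyses including the confidence intervals calculated will be of a descriptive sense".

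**The concern.** A proportion treats every child as one equal unit of observation. Here a November child is at risk of a countable event for 150 nominal days and a January child for 90. A child who stops after one or two doses has 30 or 60 days, and one given a replacement dose on Day 150 is counted to about Day 180. The same count out of 50 can therefore rest on quite different amounts of follow-up, and the headline result does not show which.

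This would matter most with few or no events, because the upper limit is then the main quantitative result. That case is realistic: Protocol 3.0 reports an earlier Russian study of 100 infants with no RSV hospitalization. Protocol 3.0 also cites 4.8% and 5.3% from trials giving five monthly doses, and a reader may set a mixed three-to-five-dose proportion beside them.

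**Working it through.** **Inputs.** N = 50 (SAP 4.3). Doses 30 days apart, numbering 5, 4 or 3 by entry month (Protocol 5.5.4, Table 1). Endpoint window to 30 days after the last dose (SAP 10.2). Exposure to 100 days after the last injection (SAP 9.0). The documents give no enrollment split, so limiting cases are shown. A child-month is 30 days.

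**1. The plan's own figures.** Clopper-Pearson limits for n = 50 are:
- 0 events: 0 to 7.11%
- 1 event: 0.05 to 10.65%
- 2 events: 0.49 to 13.71% (width 13.2 points)
- 3 events: 1.255 to 16.55%

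These match SAP 4.3, except that the last lower limit rounds to 1.3% where the SAP prints 1.2%. Nothing depends on that.

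**2. Windows.** Window = 30 × (doses − 1) + 30 days, giving 150, 120 and 90 days for 5, 4 and 3 doses.

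**3. What a rate would show.** Child-months are 50 × 5 = 250 (all November), 50 × 4 = 200 (equal thirds, mean window 120 days) and 50 × 3 = 150 (all January). With 0 events the exact Poisson upper limit is χ²(0.975; 2 df)/2 = 3.689 divided by child-time.

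| Entry | Child-months | 0 events: upper limit per 100 | 2 events: rate per 100 (95% CI) |
|---|---|---|---|
| All November | 250 | 1.48 | 0.80 (0.10 to 2.89) |
| Equal thirds | 200 | 1.84 | 1.00 (0.12 to 3.61) |
| All January | 150 | 2.46 | 1.33 (0.16 to 4.82) |

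The crude results stay at 0% (upper limit 7.1%) and 4.0% (0.5 to 13.7%) throughout. If 5 of 50 stop after one dose and the rest are in equal thirds (assumed), child-time is 45 × 4 + 5 × 1 = 185 and the zero-event limit is 3.689/185 = 1.99 per 100.

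**4. Is child-time lost from the report?** No. Nominal exposure in SAP 9.0 is 30 × (doses − 1) + 100 = 220, 190 or 160 days, which is 70 days more than the endpoint window in each case. SAP 9.0 analyses it as a continuous variable, overall and by enrollment month, and SAP 11.1 calls for the mean and the number of non-missing values. Child-days on the endpoint clock are therefore n × mean − 70n. For equal thirds the mean is (220 + 190 + 160)/3 = 190, and 50 × 190 − 70 × 50 = 6,000 days = 200 child-months. The same sum gives 250 for all November (50 × 220 − 3,500 = 7,500 days) and 150 for all January (50 × 160 − 3,500 = 4,500 days). With no events there is nothing to censor at an event, so the limits in step 3 follow from planned output, apart from children lost or withdrawn. With two events, censoring removes at most 2 × 5 = 10 child-months, or 5% of 200.

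**5. Would the rate be free of enrollment mix?** Assume 4.8% risk over November to March (the palivizumab arm of the first placebo-controlled trial in Protocol 3.0) and four illustrative ways of spreading the hazard over the five months. The table compares equal thirds with all-November entry (crude 4.80%, rate 0.984 per 100 child-months).

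| Assumed monthly shares (%) | Crude proportion | Change | Pooled rate per 100 | Change |
|---|---|---|---|---|
| Flat 20/20/20/20/20 | 3.86% | −20% | 0.984 | 0% |
| Mid-season peak 10/20/40/20/10 | 4.17% | −13% | 1.066 | +8% |
| Early peak 35/30/20/10/5 | 3.22% | −33% | 0.820 | −17% |
| Late peak 5/15/20/30/30 | 4.41% | −8% | 1.127 | +15% |

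The rate moves less than the proportion in three shapes and more in the fourth. The crude shift runs from 4.80 − 4.41 = 0.4 to 4.80 − 3.22 = 1.6 points.

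**The case for a change.** The best case for adding the rate is this. The plan breaks doses, volume, exposure and compliance down by enrollment month but not its primary endpoint. The only duration it tabulates runs 70 days past the endpoint window, so a reader who divided by it unconverted would overstate the time at risk. Child-time behind the same headline can differ by up to 250/150 = 1.67-fold. The remedy is a paragraph and a small table from dates already collected, and fixing the definition before database lock avoids a choice made after the results are seen.

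Much of this stands as description. No planned output links RSV hospitalization to time at risk, and the conversion from the 100-day to the 30-day clock is left to the reader. It does not show that the planned result misleads. The 1.67-fold contrast needs all 50 children to enter in a single month. The two-event rate intervals in the limiting cases overlap almost entirely. Table 1 places the last scheduled dose in March for all three cohorts, so on-schedule windows end at about the same point of the season and differ mainly in their start; risk over each child's own prophylaxis course is a coherent quantity. With 0 to 3 events, each RSV admission is also a serious adverse event (Protocol 6.1.1.2) and would be listed individually under SAP 11.2.2, although that listing is not said to show enrollment month.

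**Conclusion.** No change to the plan follows. The proportion and its interval are valid for the endpoint as defined. The study is non-controlled and descriptive, and no decision rule or formal comparison depends on the figure. Nominal child-time, overall and by entry month, can be recovered from SAP 9.0 by subtracting 70 days per child, and SAP 8.0 already gives enrollment by month and discontinuations by reason.

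The rate would not settle the question either. It adjusts for length of follow-up but not for season, and under the assumed late peak it shifts by 15% where the proportion shifts by 8%. Neither figure is a full-season risk. The crude shift of 0.4 to 1.6 points is small beside the 13.2-point interval at 2 events in 50.

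These sizes rest on nominal 30-day dosing, an assumed 4.8% season risk, four assumed season shapes and enrollment splits that the documents do not give. An analyst who prints child-time and a rate beside the proportion would do no harm, but the plan's conclusion is sound without them.

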### **10.3 Secondary Effectiveness Analyses**

The following secondary effectiveness variables will be summarized descriptively for all subjects with RSV hospitalization (including new onset of nosocomial respiratory/cardiac symptoms):

- Total number of RSV-hospitalization days;
- Use of increased supplemental oxygen (defined as a new requirement or an increase in supplemental oxygen from prior to the onset of cardiac/respiratory symptoms);
- Total RSV-hospitalization days with increased supplemental oxygen requirement;
- Number of ICU admissions during RSV-hospitalization;
- Total days of RSV-ICU stay;
- Use of mechanical ventilation;
- Total days of mechanical ventilation during RSV-hospitalization.

In case of only one RSV hospitalization in the study, a listing of the above information instead of descriptive summary information will be provided.

Only data corresponding to RSV hospitalization admissions and new onset of nosocomial respiratory/cardiac symptoms that occur within 30 days after the last study drug dose will be included in the analyses.

### **10.4 Other Effectiveness Analyses**

Not applicable.

### **10.5 Handling of Multiplicity**

Not applicable since this is an open-label non-comparative study.

## **10.6 Effectiveness Subgroup Analysis**

Not applicable.

## **11.0 Safety Analysis**

### **11.1 General Considerations**

All safety analyses will be done for the safety set.

All variables will be described by statistical characteristics. Categorical data will be described by frequency and percentage, quantitative data by mean, standard deviation, minimum, median and maximum. Also the number of non-missing values will be given.

### **11.2 Analysis of Adverse Events**

#### **11.2.1 Treatment-Emergent Adverse Events**

##### **Definition for Treatment-Emergent Adverse Events**

Treatment-emergent adverse events (TEAEs) will be summarized for two time spans. TEAEs are defined as any event with an onset date that is after the first dose of study drug and with an onset date no more than 30 or 100 days, respectively, after the last dose of study drug. All of the below analyses will be provided for both, the 30-day and the 100-day definition for TEAEs. Events where the onset date is the same as the study drug start date are assumed to be treatment-emergent. If an incomplete onset date was collected for an adverse event, the event will be assumed to be treatment-emergent unless there is other evidence that confirms that the event was not treatment-emergent (e.g., the event end date was prior to the study drug start date).

##### **Terms to be Summarized**

TEAEs will be summarized and presented using primary MedDRA system organ classes (SOCs) and preferred terms (PTs) according to the most current implemented MedDRA version. The system organ classes will be presented in alphabetical order and the preferred terms will be presented in alphabetical order within each system organ class.

## Summary Tables

### 1. Adverse Event Overview

The number and percentage of subjects experiencing TEAEs will be summarized for the following adverse event categories.

- Any TEAE
- Any TEAE that was rated by the investigator to have a "reasonable possibility" for a relationship to study drug.
- Any treatment-emergent severe adverse event.
- Any treatment-emergent serious adverse event.
- Any TEAE leading to discontinuation of study drug.
- Any TEAE leading to death.

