6.1.3 Relationship to Study Drug

The investigator will use the following definitions to assess the relationship of the adverse event to the use of study drug:

Reasonable Possibility	An adverse event where there is evidence to suggest a causal relationship between the study drug and the adverse event.
No Reasonable Possibility	An adverse event where there is no evidence to suggest a causal relationship between the study drug and the adverse event.

For causality assessments, events assessed as having a reasonable possibility of being related to the study drug will be considered "associated." Events assessed as having no reasonable possibility of being related to study drug will be considered "not associated." In addition, when the investigator has not reported causality or deemed it not assessable, AbbVie will consider the event associated.

[figure not shown]
If an investigator's opinion of no reasonable possibility of being related to study drug is given, an Other cause(s) of event must be provided by the investigator for the adverse event.

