8.1.6 Adverse Events

Adverse events will be coded using the current version of MedDRA (Medical Dictionary for Regulatory Activities), International Federation of Pharmaceutical Manufacturers Associations (IFPMA), Geneva, Switzerland. Treatment-emergent adverse events will be defined as those occurring after study drug initiation and within 100 days after the last dose of study drug.

The following subgroups of treatment-emergent adverse events will be summarized with frequencies and percentages by System Organ Class and Preferred Term: all events; events with probable, possible, or unknown relationship to study drug; events resulting in death; serious adverse events; and events resulting in study discontinuation. In these analyses, each subject will be counted no more than once for each Preferred Term.

Treatment-emergent adverse events will also be summarized with frequencies and percentages using the following groupings of adverse events: by System Organ Class, Preferred Term and severity; and by System Organ Class, Preferred Term and relationship to study drug. For analyses by severity, the most severe adverse event for each Preferred Term will be selected for each subject. For analyses by relationship to study drug, the event with the strongest relationship to study drug for each Preferred Term will be selected for each subject.

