### **3.0 Introduction**

This analysis plan reflects Study Protocol M15-539 dated 21 January 2016, including Amendment 1 dated 25 May 2016. It takes into account the ICH Guidelines E3 and E9.

The SAP will provide details to further elaborate statistical methods as outlined in the protocol and will describe analysis conventions to guide the statistical programming work. The SAP will be signed off before the database lock.

All data will be verified and validated according to the latest version of the integrated data review plan (IDRP).

The analysis will be performed by AbbVie using SAS® in a UNIX environment, the release currently implemented at the time of analysis.

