### 2. Adverse Events by System Organ Class and Preferred Term

The number and percentage of subjects experiencing TEAEs will be tabulated according to the primary MedDRA system organ class (SOC) and MedDRA preferred term for each treatment group. Subjects reporting more than one adverse event for a given MedDRA preferred term will be counted only once for that term (most severe incident for the severity tables and most related incident for the relationship tables). Subjects reporting more than one type of adverse event within a SOC will be counted only once for that SOC. Subjects reporting more than one type of adverse event will be counted only once in the overall total. In addition, the number and percentage of adverse events rated by the investigator as having a relationship to study drug with a "reasonable possibility" will be summarized using the same conventions described above.

A listing of subject numbers associated with AEs by SOC and PT will be provided.

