#### 4. Adverse Events by Maximum Relationship

Adverse events will also be summarized by maximum relationship to study drug, as assessed by the Investigator. If a subject has an adverse event with unknown relationship, then the subject will be counted in the relationship category of "unknown," even if the subject has another occurrence of the same event with a relationship present. The only exception is if the subject has another occurrence of the same adverse event with a relationship assessment of "reasonable possibility." In this case, the subject will be counted under the "reasonable possibility" category.

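### Two SAP summaries of drug-related TEAEs leave out events of unknown causality, which the protocol counts as related

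*SAP*

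**What the plan says.** **Protocol.** Section 8.1.6 lists the groups of treatment-emergent adverse events (TEAEs) to be tabulated by System Organ Class (SOC) and Preferred Term (PT). One of them is "events with probable, possible, or unknown relationship to study drug". Section 6.1.3 defines a two-level investigator rating (*reasonable possibility* / *no reasonable possibility*) and adds that "when the investigator has not reported causality or deemed it not assessable, AbbVie will consider the event associated".

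**SAP 11.2.1.** Three outputs deal with relationship to study drug:

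- Item 1, the overview, has a row for "Any TEAE that was rated by the investigator to have a 'reasonable possibility' for a relationship to study drug".
- Item 2, the SOC/PT tables, says that "adverse events rated by the investigator as having a relationship to study drug with a 'reasonable possibility' will be summarized using the same conventions".
- Item 4, the maximum-relationship table, keeps the unrated events in their own group: "If a subject has an adverse event with unknown relationship, then the subject will be counted in the relationship category of" *unknown*, unless another occurrence of the same event was rated *reasonable possibility*.

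Under the SAP's TEAE definition, "All of the below analyses will be provided for both, the 30-day and the 100-day definition for TEAEs". SAP 3.0 describes the document's purpose: "The SAP will provide details to further elaborate statistical methods as outlined in the protocol".

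**The concern.** The protocol's related-event summary has three components: probable, possible and unknown. The SAP's counterpart has one, the investigator's positive rating. Recasting *probable* and *possible* on the two-level scale is a reasonable translation. Dropping *unknown* is not part of that translation, because the section that defines the two-level scale is also the one that says unrated events are considered associated. Removing a component of a planned summary goes beyond elaborating the protocol's methods, and the SAP does not explain it.

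Safety is part of the stated objective (protocol 4.0, SAP 4.1). Related events may be few in a study of about 50 infants, so one unrated event could decide whether the related-event row reads none or one. If that happens, the SAP's row will disagree with the protocol-defined summary and the report will offer no explanation.

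**Working it through.** **1. The rules side by side**

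| Source | Counted as related | Unknown, missing or non-assessable |
|---|---|---|
| Protocol 6.1.3 | *reasonable possibility* | considered associated |
| Protocol 8.1.6, SOC/PT summary | probable, possible | included |
| SAP 11.2.1 item 1, overview row | *reasonable possibility* | not included |
| SAP 11.2.1 item 2, related SOC/PT table | *reasonable possibility* | not included |
| SAP 11.2.1 item 4, maximum relationship | *reasonable possibility* | separate category |

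The SAP expects unrated events to occur, since item 4 provides a category for them. In that table *unknown* gives way only to *reasonable possibility*, so it ranks above *no reasonable possibility*. Items 1 and 2 nevertheless handle it as not related. The SAP is more cautious about incomplete onset dates, where the event is assumed treatment-emergent unless other evidence shows that it was not.

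**2. Outputs affected**

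2 summaries (items 1 and 2) × 2 TEAE windows (30-day and 100-day) = 4.

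**3. Direction and size**

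Neither document gives a related-event rate, so there is no planned figure to reproduce. The following is an illustration, with these inputs:

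- N = 50, the anticipated enrolment (SAP 4.3).
- r = children with at least one TEAE rated *reasonable possibility*.
- k = children with no such event but at least one TEAE of missing or non-assessable causality. The documents do not give k, so a range of 0 to 3 is assumed.

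Formulas:

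- SAP rate = r/N
- Protocol rate = (r + k)/N
- Difference = k/N = k/50, or 2 percentage points per child. It cannot be negative.

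| r | k | SAP | Protocol rule |
|---|---|---|---|
| 0 | 0 | 0% | 0% |
| 0 | 1 | 0% | 2% |
| 0 | 3 | 0% | 6% |
| 1 | 0 | 2% | 2% |
| 1 | 1 | 2% | 4% |
| 1 | 2 | 2% | 6% |
| 1 | 3 | 2% | 8% |

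**4. Precision, for scale only**

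The exact (Clopper-Pearson) 95% limits for x of n are the 2.5% quantile of Beta(x, n − x + 1) and the 97.5% quantile of Beta(x + 1, n − x). The lower limit is 0 when x = 0. For n = 50:

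- x = 0: 0 to 7.11%
- x = 1: 0.05 to 10.65%
- x = 2: 0.49 to 13.71%
- x = 3: 1.25 to 16.55%

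These agree to within 0.1 percentage point with the limits in SAP 4.3 (0; 7.1%, 0.1; 10.6%, 0.5; 13.7%, 1.2; 16.5%). With r = 0 and k = 1, the SAP row shows 0/50 (0 to 7.1%) and the protocol's rule gives 1/50 = 2% (0.1 to 10.6%).

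**5. Can the protocol's count be recovered from item 4?**

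Within a single preferred term it can, if the table is laid out by SOC and PT: add the *reasonable possibility* and *unknown* counts. The override prevents double counting within the term. For SOC and overall subject totals it cannot be relied on. The override is written for occurrences of the same event, and the SAP does not say how to classify a child who has one event rated *unknown* and a different event rated *reasonable possibility*.

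**The case against.** The strongest reply is that nothing is hidden. Unrated events appear in the maximum-relationship table for both windows, and serious events and those leading to discontinuation are also listed. The two SAP rows are labelled as investigator ratings and count exactly what they name. Protocol 6.1.3 states how the sponsor will regard an unrated event, not how a row of investigator ratings must be built. Protocol 8.1.6 uses terms that this trial does not collect, so the SAP had to translate. Protocol 6.1 requires the investigator to record relationship for every event, and eCRFs are reviewed for completeness, so k may well be zero. The study is descriptive and no decision depends on this row. The SAP plans no confidence interval for adverse event rates.

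Most of this is fair and limits the point. The information is not lost, the labels are accurate, the effect may be nil, and the intervals above only give scale. The related SOC/PT sentence in the SAP also speaks of the number and percentage of adverse events. The 2-point step therefore applies to that table only if its reference to the same conventions means counting subjects.

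What remains is the departure itself. An accurate label on a narrower row does not supply the summary that protocol 8.1.6 planned. Translating the scale accounts for *probable* and *possible*, but not for the loss of *unknown*. Subject totals for the protocol's grouping cannot be dependably rebuilt from the maximum-relationship table.

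**Conclusion.** The concern holds. As written, SAP 11.2.1 does not produce the related-event summary of protocol 8.1.6, and it handles unrated causality differently from protocol 6.1.3 without giving a reason. The gap is confined to the overview row and the related SOC/PT table, four outputs in all.

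The count under the SAP can be lower than the protocol's and never higher. That direction rests on mapping *probable* and *possible* to *reasonable possibility*, which is sensible but stated in neither document. The size is 2 percentage points per affected child at N = 50, and zero if every event carries a rating. This should be corrected, but its effect on the results is conditional and may be nil.

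**What to change.** Change SAP 11.2.1 only, before the SAP is signed off ahead of database lock:

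1. In the overview row and the related SOC/PT table, define a drug-related TEAE as one rated *reasonable possibility* or one whose causality is missing or not assessable.
2. Show the investigator-rated *reasonable possibility* subset as a sub-line, so that the count the SAP now plans is kept.
3. Footnote the maximum-relationship table to say that *unknown* is considered associated under protocol 6.1.3.
4. State that *probable* and *possible* in protocol 8.1.6 correspond to *reasonable possibility* on the two-level scale of protocol 6.1.3.

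The cost is some SAP wording, one derivation line, one sub-line and one footnote. No protocol amendment and no new data are needed. The only downside is that the reported related-event percentage may be slightly higher.
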